Effectiveness Endpoint: The effectiveness endpoint is the rate of effective closure of the PDA using a transcatheter device within six months post procedure. If more than one attempt is required, or multiple devices are required during the same procedure, it is still considered effective if there is Grade 0 or Grade 1 shunt, as defined below, at follow-up (within six months) by transthoracic echocardiography (TTE) or if a second procedure is not required following the initial attempt. If there is device embolization, adjacent vessel stenosis that required retrieval of the device and replacement during the same procedure with less than Grade 1 shunt during follow-up, it is still considered effective. Conversely, if an AE is noted after the procedure that requires a second procedure for treatment that results in greater than Grade 1 shunt, then the procedure is considered not effective, even if the initial attempt was effective.

PDA shunt definition:

Grade 0—none;

Grade 1—trivial (narrow jet adjacent to the device via the PDA). Note: the presence of flow via existing or newly formed aortopulmonary collaterals should not be considered as representing a shunt via the PDA. (See references in **Appendix B** by Skinner and Acherman)

Grade 2—mild (broader jet filling proximal left pulmonary artery branch and extending to main pulmonaryartery);

Grade 3/4—moderate to severe (wide jet filling the main pulmonary artery and extending to pulmonary valve or distal pulmonary artery branches, which also may be accompanied with the presence of flow reversal in the abdominal aortic Doppler pattern during diastole)

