7.2 Primary Effectiveness Endpoint

The primary effectiveness endpoint is the rate of effective closure of the PDA among subjects with a successful device implant as assessed by the presence of either a Grade 0 or Grade 1 shunt (see **Appendix A** for definition) at the 6 month follow-up visit by transthoracic echocardiography.

The proportions of subjects who have effective closure of the PDA at follow-up will be calculated along with the 95% confidence interval. The numerator for the event rate is the number of subjects who have effective closure of the PDA at follow-up. The denominator is the number of subjects in the analysis population (As detailed in Section 7.4). The primary effectiveness endpoint will be compared with the rate reported in the ADO II AS and Continued Access Protocol studies.

Among subjects successfully implanted with any device, the PDA occlusion rate is estimated to be approximately 99%.

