7.4 Analysis Population

The analysis of the primary and secondary endpoints will include all subjects who achieve a successful implant, which is defined as leaving the catheterization lab with a device implanted in the PDA. If a subject has multiple devices attempted during the same procedure, but leaves procedure with at least one device within the PDA the procedure is considered successful. Subjects without an implanted device in the PDA will be excluded. Additionally, subjects who had no follow- up visits up to the six-months +/- one-month window, or lost to follow-up will be excluded.

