APPENDIX D: ADVERSE EVENT REPORTING FORM

ADVERSE EVENT FORM

Type of adverse event:
Device embolization Access complications Vessel stenosis Valve injury Other
Device embolization:
During the procedure (In the cath lab): Yes 🔜 No 🔜
After the procedure (In recovery): Yes 🔜 No 🔜
Delayed embolization (>24 hours later): Yes 🦲 No 🦲
Embolization site:
Left pulmonary artery Right pulmonary artery
Aorta/systemic artery Right ventricle Other site (Specify)
Outcome of embolization:
Observation only
Successful transcatheter retrieval with PDA occlusion with another device
Successful transcatheter retrieval, PDA not occluded with another device
Successful transcatheter retrieval, PDA surgically ligated
Unsuccessful transcatheter retrieval, PDA occlusion with another device
Unsuccessful transcatheter retrieval, PDA not occluded with another device
Unsuccessful transcatheter retrieval, PDA surgically ligated
Device embolization led to initiation of inotropic suport
Device embolization led to initiation of mechanical circulatory support
Device embolization led to patient mortality
Access complications:
During the procedure (In the cath lab): Yes No
After the procedure (In recovery): Yes No
Delayed access complication (>24 hours later): Yes No
Arterial access complication:
Transient loss of pulse with spontaneous recovery without intervention
Transient loss of pulse with recovery following intervention
Non-occlusive arterial thrombus – No intervention needed/performed
Non-occlusive arterial thrombus – Requiring intervention
Occlusive arterial thrombus – Requiring intervention
Medical Surgical
Loss of limb secondary to vascular access complication
Venous thrombosis – anticoagulation/antiplatelet therapy performed
Venous thrombosis – anticoagulation/antiplatelet therapy not performed

Vessel stenosis:

Noted during the procedure (In the cath lab): Yes Noted after the procedure (In recovery): Yes Delayed finding (>24 hours later): Yes

No	
No	
No	

Left pulmonary artery stenosis:

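### The primary effectiveness endpoint does not make a later procedure to close the duct a failure of the index Piccolo implant, and Sections 2.1 and 7.2 conflict on surgical ligation

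*Protocol*

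**What the plan says.** Section 2.1 opens the effectiveness endpoint with "The effectiveness endpoint is the rate of effective closure of the PDA using a transcatheter device within six months post procedure". It then gives scoring rules:

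- Where more than one attempt or several devices are needed, "it is still considered effective if there is Grade 0 or Grade 1 shunt" on follow-up echocardiography, "or if a second procedure is not required following the initial attempt".
- For embolization, or narrowing of an adjacent vessel, the rule reads: "required retrieval of the device and replacement during the same procedure with less than Grade 1 shunt during follow-up, it is still considered effective".
- In the other direction, for an adverse event found afterwards, the rule reads: "requires a second procedure for treatment that results in greater than Grade 1 shunt, then the procedure is considered not effective".

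Section 7.2, which defines the analysis, takes closure "among subjects with a successful device implant as assessed by the presence of either a Grade 0 or Grade 1 shunt" at the 6-month visit. It sets no condition on how closure was achieved.

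Section 7.4 admits infants with a successful implant, meaning "leaving the catheterization lab with a device implanted in the PDA". It excludes those with no device in the duct and those without follow-up. Nothing removes an infant who has a further procedure later.

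The adverse event form in Appendix D provides, under embolization, for "Successful transcatheter retrieval, PDA surgically ligated", with a parallel box for closure with another device. The safety endpoint text in Section 2.1 also foresees embolization and stenosis found more than 24 hours after the procedure, and retrieval on a separate occasion.

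**The concern.** Sections 1 and 1.1 set out to show that transcatheter closure with the Piccolo is effective. An infant whose device had to be removed and replaced days later, or whose duct was closed by another route, is a failure of the index implant on any ordinary reading of that objective. If such infants enter the numerator, the endpoint measures whether the duct is closed at 6 months by whatever means, not whether the implanted device closed it.

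The protocol expects about 99% closure, so failures are few and a handful of reclassified infants changes the failure rate by a large factor. Sections 7.2 and 7.6 also plan to set the result beside earlier studies of the device, which needs a rate with one clear meaning.

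**Working it through.** **Step 1. Score the possible cases under each section.** All infants except those in the last row left the lab with a device in the duct and have follow-up.

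| Case | Section 2.1 | Section 7.2 |
|---|---|---|
| Device replaced in the index procedure, Grade 0 at follow-up | Effective | Effective |
| Adverse event, later second occluder, Grade 0/1 at 6 months | Failure rule not triggered; Grade 0/1 limb met | Effective |
| Residual shunt only, later second occluder, Grade 0/1 | Failure rule does not apply (no adverse event); Grade 0/1 limb met | Effective |
| Adverse event, later surgical ligation, Grade 0 | Failure rule not triggered, but outside the opening sentence (not closed by a transcatheter device) | Effective |
| Adverse event, second procedure, shunt above Grade 1 at 6 months | Not effective | Not effective |
| No device in the duct on leaving the lab | Outside the analysis (7.4) | Outside the analysis (7.4) |

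Rows 2 and 3 show a later second occluder escaping failure under both sections. Row 4 shows the two sections disagreeing on the same infant.

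**Step 2. Size, as an illustration only.** There is no planned figure to reproduce: Section 7.6 states no formal hypothesis, and 500 is a limit on data collection.

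Inputs:
- N = 500 (Section 2). The analysed number will be smaller after the 7.4 exclusions.
- Closure about 99% (Section 7.2, stated there for any device), so C = 0.99 × 500 = 495 closed ducts and 5 open.
- R = infants among the 495 whose duct was closed by a later procedure. The protocol gives no figure; about 0.5% to 5% of N is assumed.

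Rate as written = C/N. Rate with later procedures scored as failures = (C − R)/N. Failures are multiplied by (N − C + R)/(N − C). Intervals are exact binomial for x successes in n: lower limit = Beta quantile(0.025; x, n − x + 1), upper limit = Beta quantile(0.975; x + 1, n − x). The protocol names the exact method in 7.1 only; it is used here for convenience.

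| R (assumed) | Share of N | (C − R)/N | 95% CI | Failures multiplied by |
|---|---|---|---|---|
| 0 | 0% | 495/500 = 99.0% | 97.7 to 99.7 | 1.0 |
| 2 | about 0.5% | 493/500 = 98.6% | 97.1 to 99.4 | 1.4 |
| 5 | 1% | 490/500 = 98.0% | 96.4 to 99.0 | 2.0 |
| 10 | 2% | 485/500 = 97.0% | 95.1 to 98.3 | 3.0 |
| 15 | 3% | 480/500 = 96.0% | 93.9 to 97.5 | 4.0 |
| 25 | 5% | 470/500 = 94.0% | 91.6 to 95.9 | 6.0 |

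At R = 10, the rate with later procedures as failures (97.0%) lies below the lower limit of the interval that would be reported (97.7%). With fewer analysed infants the picture is similar: at n = 400, 396/400 = 99.0% (97.5 to 99.7) becomes 392/400 = 98.0% (96.1 to 99.1) with 4 such infants.

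Since R cannot be negative, the rate as written is never below the alternative.

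**The case against.** The best defence is that Section 2.1 was meant to treat later procedures as failures. It limits closure to a transcatheter device, twice confines its tolerance to events within the same procedure, and mentions the absence of a second procedure. The sentence on failures names one failing case without saying that every other second procedure succeeds. Section 7.2 can be read as shorthand for the term that 2.1 defines.

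Part of this stands. A reader might infer that the protocol plainly counts a surgically ligated duct as a device success. It does not: the opening sentence of 2.1, read literally, excludes it, and the fault there is a conflict with 7.2. For a second occluder the defence fails, because that sentence is limited neither to the Piccolo nor to the index procedure, the limb on second procedures is joined by *or*, and no sentence scores such a case as a failure. Intent that can only be guessed does not settle a primary endpoint.

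A reader might also infer that the comparison with the IDE and Continued Access studies is biased. The protocol does not give their scoring rule. If they treated later procedures in the same way, the comparison would be like with like.

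Finally, the study is descriptive, and related events that need major open surgery under general anesthesia would appear among the major complications. That limits the harm. It does not make the closure rate itself correct.

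**Conclusion.** The point holds in this form. Neither section makes a later procedure to close the duct a failure of the index implant. A later second occluder that leaves Grade 0 or 1 passes under both; a later ligation passes under 7.2 and not under the opening sentence of 2.1. Compared with scoring such infants as failures, the rules as written can only raise the primary effectiveness rate.

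The amount cannot be derived from the protocol, because it gives no frequency of later procedures. The doubling of failures at an assumed 1% follows from placing 5 such infants beside 5 open ducts in 500; it shows sensitivity and is not an estimate. The conclusion on direction needs no such assumption.

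**What to change.** Put one definition in Sections 2.1 and 7.2: effective closure is Grade 0 or 1 on transthoracic echocardiography **and** no procedure after the index procedure to close the duct or to remove or replace the device. Score any such later procedure (second occluder, retrieval, ligation) as not effective whatever the final shunt grade. Keep several attempts, or a replacement, within the index procedure as effective. Report final closure by any means as a descriptive result; this also keeps a comparison possible if the earlier studies used a different rule. The change concerns scoring only and alters nothing in patient care.

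The cost is small: a wording change in two sections and a slightly lower reported rate if such cases occur. One case report form field may also be needed. Appendix D visibly records ligation and replacement under embolization, and retrieval or replacement under vessel stenosis, but shows no specific item for later re-closure of a residual shunt without one of those events.

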2.2 Secondary Endpoints

The secondary endpoint is the rate of significant obstruction of the pulmonary artery or aorta during follow-up (within 6 months) per the following definitions:

1. Significant obstruction of the left pulmonary artery is defined as less than 30% flow to the left lung by lung perfusion scan or a peak instantaneous gradient in left pulmonary artery

 \geq 35 mmHg by echocardiogram if lung perfusion scan is not available. OR

2. Significant obstruction of the aorta is defined as a gradient of \geq 20 mmHg in the aortic isthmus by invasive aortic catheterization or a mean gradient \geq 20 mmHg in the aortic isthmus by echocardiogram if invasive aortic catheterization is not available.

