2.1 Primary Endpoint(s)

Safety Endpoint: Composite rate of major device- or procedure-related adverse events (AE) of interest through 6 months' post-implantation procedure. AEs of interest are broadly categorized as:

- a. Vascular access complications
- **b.** Valvular Injury
- **c.** Device embolization
- d. Pulmonary or aortic vessel stenosis

Access vessel complications include femoral arterial or femoral/jugular venous complications noted during the procedure, immediately after the procedure or delayed (>24 hours). They range from bleeding from access sites, arterial or venous thrombosis with or without the need for treatment to loss of limb secondary to arterial occlusion.

Valvular injury includes damage to the tricuspid valve or other cardiac valve resulting in immediate post-procedural valvular dysfunction.

Device embolization includes malposition of the device either during or after the procedure or delayed (>24 hours). The outcome of device embolization ranges from observation, transcatheter retrieval at time of procedure or at a separate time, surgical retrieval, other end organ damage, tomortality.

Adjacent vessel stenosis includes a narrowing of the aorta or the left pulmonary artery directly as a consequence of device implantation for PDA closure. Vessel stenosis could happen either during or after the procedure or delayed (>24 hours). The outcome of vessel stenosis ranges from no intervention needed to repeated transcatheter and surgical therapies.

For details of each AEs and definitions, refer to **Appendix A**.

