5.5.3 Aortic or Pulmonary Artery Stenosis

If stenosis of the aorta or pulmonary artery is suspected or noted during the procedure or during follow-up, the following measures are recommended:

- a. Perform a ortic catheterization to obtain invasive measurement of the gradient if the mean gradient by echocardiogram in the aortic isthmus is \geq 20mmHg.
- b. If aortic catheterization is contraindicated, then an alternative imaging study, such as computed tomography (CT) aortic angiography imaging or magnetic resonance (MR) aortic angiography imaging may be utilized.
- c. CT aortic angiography or MR aortic angiography may be used to confirm a significant aortic obstruction whenever there is \geq 50% diameter narrowing at the aortic isthmus.
- d. Alternatively, a clinical exam may be used to confirm aortic obstruction.
- Exam criteria = 1) Diminished lower extremity pulses or a blood pressure discrepancy of ≥ 20mmHg between the upper and lower extremities AND 2) an abnormal abdominal aortic Doppler pattern (blunted profile with diminished upstroke, holo-diastolic antegrade flow, or flow reversal during diastole).
- f. If a new significant gradient in the pulmonary artery or the aorta is identified on follow-up echocardiograms, a lung perfusion scan or CT/MR/aortic catheterization will be required to determine if the result meets the secondary endpoint.

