7.3 Secondary Endpoints

The secondary endpoint is the rate of significant obstruction of the pulmonary artery or aorta through the follow-up visit per the following definitions:

1. Significant obstruction of the left pulmonary artery is defined as less than 30% flow to the left lung by lung perfusion scan or a peak instantaneous gradient in left pulmonary artery ≥35 mmHg by echocardiogram if lung perfusion scan is not available. OR

2. Significant obstruction of the aorta is defined as a gradient of ≥ 20 mmHg in the aortic isthmus by invasive aortic catheterization or a mean gradient ≥ 20 mmHg in the aortic isthmus by echocardiogram if invasive aortic catheterization is not available.

The proportions of subjects experiencing an obstruction of the pulmonary artery or aorta through the of low-up visit will be calculated along with the 95% confidence interval. The numerator for the event rate is the number of subjects who experience an event by the follow-up visit. The denominator is the number of subjects in the analysis population (As detailed in Section 7.4).

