The adverse event is related to the study device/procedure – i.e. an event that follows a reasonable temporal sequence from administration of the study intervention, follows a known or expected response pattern to the suspected intervention, that is confirmed by improvement on stopping and reappearance of the event on repeated exposure and that could not be reasonably explained by the known characteristics of the subject's clinical state.

In summary, the AE is related to any study device or procedure if the event satisfies all of following criteria:

- a. Has a reasonable temporal relationship to intervention (e.g. device implant)
- b. Could not readily have been produced or explained by the subject's clinical state or have been due to environmental or other interventions
- c. Follows a known pattern of response to intervention
- d. Disappears or decreases with reduction in dose or cessation of intervention and recurs with re-exposure

MajorComplication

Major complications are defined as device or procedure-related adverse events resulting in any of the following:

- a. Death
- b. Life-threatening adverse event,
- c. Persistent or significant disability/incapacity, and/or
- d. A major open surgical intervention which is performed by a surgeon under general anesthesia

Examples of Major Complications:

- a. Device or procedure related events leading to death
- b. Cardiac perforation requiring percutaneous (e.g., pericardiocentesis) or open surgical intervention
- c. Cardiac tamponade
- d. Embolization requiring open surgical procedure (e.g., open heart surgery or femoral vessel cut down procedure) to retrieve the device
- e. Persistent hemodynamic instability requiring emergency cardioversion/defibrillation therapy or emergency blood transfusion and/or institution of inotropic therapy
- f. Excessive blood loss or hemolysis requiring transfusion > 20 cc/kg
- g. Persistent or worsening respiratory instability
- h. Cerebral or pulmonary embolism
- i. Persistent cardiac arrhythmia requiring a pacemaker
- j. Arteriovenous fistula requiring open surgical intervention
- k. False aneurysm of the femoral artery requiring surgical intervention
- l. Femoral vessel thrombophlebitis treated with intravenous antibiotics
- m. Infection of the device (bacterial endocarditis)

Minor Complication

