No intervention was required Intervention performed during the same catheterization Intervention performed within 24 hours Intervention performed > 24 hours Re-intervention on the left pulmonary artery is unlikely Re-intervention on the left pulmonary artery is likely *Type of intervention for the left pulmonary artery stenosis*: Retrieval of device with no further intervention Retrieval of device with repositioning of the same device Retrieval of device with use of a different device Balloon angioplasty of the left pulmonary artery stenosis Surgical repair

Descending aorta stenosis:

No intervention was required Intervention performed during the same catheterization Intervention performed within 24 hours Intervention performed > 24 hours Re-intervention on the aorta is unlikely Re-intervention on the aorta is likely

Type of intervention for the descending aorta stenosis:

Retrieval of device with no further intervention Retrieval of device with repositioning of the same device Retrieval of device with use of a different device Balloon angioplasty of the descending aorta stenosis Stent implantation for descending aorta stenosis Surgical repair

Valve	e Injury:
	Noted during the procedure (In the cath lab): Yes No
	Noted after the procedure (In recovery): Yes 📃 No 🔜
	Delayed finding (>24 hours later): Yes No
Injure	ed Valve:
	Tricuspid valve
	Pulmonary valve
	Mitral valve
	Aortic valve
Degre	ee of regurgitation:
	Mild
	Moderate
	Severe
Mech	anism of regurgitation:
	Avulsion of chordae
	Avulsion of chordae Central non-coaptation of the valve Valve leaflet injury Injury to valve appulus
	Valve leaflet injury
	Injury to valve annulus
Outco	ome:
	Observation only
	Medical therapy
	Surgical intervention

Other complications: Bleeding into: Pericardium Pleura Peritoneum Retroperitoneum External hemorrhage Vessel perforation Cardiac arrest Arrhythmias including AV heart blocks Stroke Death Infection including suspected endocarditis and sepsis Post PDA ligation syndrome

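### The secondary obstruction endpoint counts only gradient or perfusion thresholds, so an infant treated for stenosis without a qualifying reading is counted as free of obstruction

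*Protocol*

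**What the plan says.** Section 2.2: "The secondary endpoint is the rate of significant obstruction of the pulmonary artery or aorta during follow-up (within 6 months) per the following definitions". For the left pulmonary artery the definition is "less than 30% flow to the left lung by lung perfusion scan or a peak instantaneous gradient in left pulmonary artery" of at least 35 mmHg by echo, the echo value applying when no scan is available. For the aorta it is an isthmus gradient of at least 20 mmHg by catheterization, or a mean gradient of at least 20 "mmHg in the aortic isthmus by echocardiogram if invasive aortic catheterization is not available". Sections 2.2, 7.3 and Appendix A agree, and none mentions intervention.

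Section 7.3 fixes the count: "The numerator for the event rate is the number of subjects who experience an event by the follow-up visit". The denominator is the 7.4 population: infants who leave the laboratory with a device in the duct and have follow-up.

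The protocol expects some stenoses to be treated. Section 2.1: "The outcome of vessel stenosis ranges from no intervention needed to repeated transcatheter and surgical therapies". The adverse event form in Appendix D records device retrieval, balloon angioplasty and surgical repair for each vessel, and for the aorta also "Stent implantation for descending aorta stenosis", with timing categories.

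Section 5.5.3 gives further routes to a finding of aortic obstruction: CT or MR showing at least 50% narrowing, and "Alternatively, a clinical exam may be used to confirm aortic obstruction". Its item f makes a perfusion scan or CT/MR/catheterization decisive for whether a new gradient meets the secondary endpoint.

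**The concern.** A stenosis judged to need a balloon, a stent or removal of the device is one that a reader would expect an obstruction endpoint to reflect. Under the written rule it enters only if a qualifying measurement was also made. The protocol does not ensure one. Section 4.4 says echo must be obtained within 48 hours and at 1 and 6 months. Sections 3.1 and 4 say no special testing is required, and 8.1 allows missing echo details not to count as a deviation.

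The primary safety endpoint closes the gap only in part. It counts major events, and the Appendix A criterion that concerns treatment is "A major open surgical intervention which is performed by a surgeon under general anesthesia". A balloon or stent is not major by itself; the event must also be fatal, life-threatening or disabling. An infant treated by catheter without a qualifying reading can therefore be absent from both the primary safety rate and the secondary obstruction rate.

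**Working it through.** The protocol gives no expected obstruction rate and no sample-size calculation, so there is no stated figure to reproduce. The check has two parts.

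**1. Where a treated infant is counted**

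| Infant | Secondary endpoint (2.2, 7.3) | Elsewhere |
|---|---|---|
| Qualifying reading within 6 months, then treated | Counted; the endpoint is cumulative | Major or minor complication, if related |
| Device removed at the index procedure, none left in place | Excluded by 7.4 | Outside both rates |
| Open surgery under general anesthesia after the index procedure, no qualifying reading | Not counted; in the denominator | Major complication, if related; in the primary safety rate |
| Balloon, stent or catheter device removal after the index procedure, no qualifying reading, no other major criterion | Not counted; in the denominator | Minor complication under 7.5d, if related; not in the primary safety rate |
| Aortic obstruction confirmed only by CT/MR or examination | Unclear: 5.5.3 and the definitions disagree | Depends on treatment and severity |

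The third and fourth rows are the gap for the secondary endpoint. Only the fourth is missed by both endpoints. Section 7.5c does not help, because it applies the 7.3 definition at the 6-month visit.

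**2. Size**

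Let x be the infants meeting a threshold, k those treated without a qualifying reading, and n the analysis population. The existing rule gives x/n; counting treatment gives (x + k)/n; the difference is k/n. Each infant adds 1/500 = 0.20 percentage points at n = 500 and 1/400 = 0.25 at n = 400.

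The 500 is the initial cohort in section 2. The 400 is an assumed smaller population after the 7.4 exclusions, and x and k are also assumed. Intervals are exact (Clopper-Pearson) 95%.

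| n | x | k | By thresholds, x/n | Thresholds or treatment, (x + k)/n |
|---|---|---|---|---|
| 500 | 0 | 3 | 0% (0 to 0.74) | 0.6% (0.12 to 1.74) |
| 500 | 5 | 1 | 1.0% (0.33 to 2.32) | 1.2% (0.44 to 2.59) |
| 500 | 5 | 3 | 1.0% (0.33 to 2.32) | 1.6% (0.69 to 3.13) |
| 500 | 5 | 5 | 1.0% (0.33 to 2.32) | 2.0% (0.96 to 3.65) |
| 500 | 10 | 5 | 2.0% (0.96 to 3.65) | 3.0% (1.69 to 4.90) |
| 400 | 5 | 5 | 1.25% (0.41 to 2.89) | 2.5% (1.21 to 4.55) |

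If k = 0 the two rates are equal.

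**The case against.** The case for leaving the endpoint alone has several parts.

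- **Treatment does not erase an event.** A reader might infer that a treated infant is lost because later gradients are normal. The text does not support that: 2.2 and 7.3 count any event through follow-up, so a qualifying reading before treatment counts permanently. This stands and limits the gap to infants with no reading or only sub-threshold ones.
- **The 5.5.3 routes often start from a qualifying reading.** A reader might infer that an infant confirmed by CT, MR or examination can never meet 2.2. That goes too far. Item a starts from an echo mean gradient of at least 20 mmHg, and where catheterization is contraindicated under item b, that echo value already satisfies the definition. The examination route requires a Doppler pattern, so it does not imply that no gradient was measured. What remains is that items c to f use criteria the definitions do not contain.
- **Treated infants are still reported.** Related open surgery is major, and other related catheter treatment appears among minor complications in 7.5d. This stands, but 7.5d does not report those infants as obstruction.
- **A fixed threshold is a legitimate choice.** Treatment follows each site's practice, so counting it brings in operator judgement, and a stenosis treated below threshold is not significant by the stated definition. This is a fair reason to keep the threshold rate. It is not a reason to withhold the second rate.
- **The statistical analysis plan may settle it.** That plan is not shown, but the protocol states a complete counting rule in three places, so this is not a detail left open.

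**Conclusion.** The point holds in limited form. For the secondary endpoint, any treatment after the index procedure without a qualifying reading is counted as no obstruction. For the secondary and primary safety endpoints together, the gap is confined to catheter or device-removal treatment that meets no major criterion.

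The size is about 0.2 percentage points per infant at n = 500. In the assumed case of 5 threshold events in 500, five such infants would double the reported rate, from 1.0% to 2.0%, with overlapping intervals. How many there will be cannot be learned from the protocol. The combined rate can only equal or exceed the threshold rate. Calling the difference bias would assume that every intervention proves significant obstruction, which the protocol does not say.

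The study has no formal hypothesis (7.6), so no decision rule changes. The mismatch between 5.5.3 and the definitions is a separate inconsistency that must be reconciled whatever the count turns out to be.

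**What to change.** Report the secondary endpoint two ways on the 7.4 population:

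1. by the existing thresholds;
2. by those thresholds or any balloon angioplasty, stent, surgical repair or device removal for left pulmonary artery or aortic stenosis, performed after the index procedure and within 6 months.

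Take the interventions from the adverse event form, whose timing categories separate treatment at the same catheterization from later treatment. State in 2.2, 7.3 and Appendix A which rate is the headline. In the same amendment, make those sections and 5.5.3 agree on whether CT/MR or examination findings count toward the endpoint. Adding the intervention rate does not settle that question, since an obstruction confirmed by imaging but left untreated would stay ambiguous.

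The cost is a short addition in three places, the alignment with 5.5.3, one extra tabulation, and a second rate that may look slightly less favourable. Section 7.3 plans no external comparison for this endpoint. Section 7.6 speaks more broadly of comparing safety results with the earlier device studies, and the threshold-only rate keeps any such comparison possible. The change concerns counting only and alters no clinical management.
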